
PROTOCOL

VERSION B

SECTION 1 – TITLE, PURPOSE AND JUSTIFICATION

- **1.1 Title.** Safety and Efficacy of Thymic Peptides in the Treatment of Hospitalized COVID-19 Patients in Honduras.
- **1.2 Study Purpose.** To determine if thymic peptides (Unicahsina) are a new therapeutic option for the treatment of patients infected by COVID-19 in order to improve their clinical prognosis.
- **1.3 Justification**. Coronaviruses are important pathogens in humans and animals, causing respiratory tract and lung parenchymal infections. In late 2019, a novel coronavirus was identified as the cause of a series of pneumonia cases in Wuhan, a city in Hubei province in China (1). The infection spread rapidly, leading to an epidemic throughout China, followed by an increasing number of cases in other countries, affecting all continents except Antarctica (1). WHO declared COVID-19 a pandemic on March 11, 2020 (2). The virus is currently referred to as Severe Acute Respiratory Syndrome Coronavirus 2 (SARS-CoV-2) and the disease caused by the virus is known as COVID-19.

At the time of writing this protocol, more than 5,584,091 cases of COVID-19 have been reported worldwide (3). This is largely due to the ease with which this virus is transmitted. The primary mechanism of spread is person-to-person transmission, which occurs primarily by respiratory droplets (1). Transmission of SARS-CoV-2 via fomites is plausible as it has been shown to remain viable on surfaces for hours and even several days (4).

The coronavirus that causes COVID-19 is a betacoronavirus of the same subgenus as SARS-CoV (5). The incubation period is estimated to be 14 days after exposure, with most cases occurring between 4 and 5 days (6-8). The disease is mild in 81% of cases, severe in 14% and critical in 5% (9). The overall mortality rate is 2.3% (9). The clinical course is characterized by fever (99%), fatigue (70%), dry cough (59%), anorexia (40%), myalgia (35%), dyspnea (31%) and sputum (27%) (10). Pneumonia appears to be the most serious manifestation of infection, characterized mainly by fever, cough, dyspnea and a bilateral pulmonary infiltrate (visible on imaging) (7, 10-12).

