Scientific evidence proves the absence of short or long-term adverse effects of thymomodulin, obtaining significant results in the treatment of patients with immunological vulnerability in various respiratory pathologies (23). Taking this into account, it can be considered a promising alternative to combat the COVID-19 pandemic. The following sections will discuss the methodology of the clinical trial that will be used to evaluate its efficacy as a therapeutic option.

Hypothesis

Oral administration of thymic peptides (Unicahsina) is a safe and effective therapy for the management of patients with COVID-19 respiratory onsets.

General Objective

To demonstrate the therapeutic efficacy and safety of thymic peptides (Unicahsina) in patients with COVID-19 respiratory disease.

Specific objectives

- 1. To evaluate the safety of thymic peptides (Unicahsina) by monitoring adverse events using the Common Terminology Criteria for Adverse Events Version 5.0 (CTCAE v5.0) and side effects using the General Assessment of Side Effects (GASE).
- 2. Determine the time to participant recovery, according to a clinical ordinal progression scale.
- 3. To perform survival analysis in patients diagnosed with COVID-19 and treated with thymic peptides (Unicahsina).

SECTION 2 - DESCRIPTION OF THE POPULATION

2.1 Number of participants: 20 participants.

2.2 Describe the population:

Patients with diagnosis of COVID-19 confirmed by RT-qPCR testing, viral antigen detection or antibody detection plus associated symptomatology. The study will be performed in patients over 20 years of age without distinction of sex, race, religion, or socioeconomic status. Since the population under 20 years of age presents mostly mild or asymptomatic symptoms, with a mortality rate between 0% and 0.2%, it was decided to exclude this age range.

This research will involve elderly patients and those with comorbidities. The current COVID-19 pandemic has shown that this group of patients has the highest mortality rate, exposing the need to discover safe and effective therapies. Therefore, and given the innocuous profile that thymic peptides possess, we consider their use in this population.

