Should any of the participants decide to withdraw from the study voluntarily or request self-discharge, another patient will be added to the study until 20 patients have reached conclusion either by medical discharge or death within a 20-day hospitalization follow-up. Patient data will be used up to the date of voluntary withdrawal or self-discharge.

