4.1 Study design

This is a single-arm, open-label, phase II clinical trial to evaluate the safety and efficacy of thymic peptides in the treatment of hospitalized COVID-19 patients in Honduras, at the Hospital de Santa Bárbara Integrado. A participant-level comparison will be made based on registry data of the Hospital de Santa Bárbara Integrado, after propensity score matching.

In total, 20 patients will be recruited from the designated hospital for COVID-19 patient care, including those who have signed informed consent and who meet the inclusion criteria. For the generation of the comparison group through data from clinical records, it will be carried out by authorization from the Hospital de Santa Bárbara Integrado, given its retrospective nature, without experimental intervention.

Clinical characterization

Once the protocol is started, the information corresponding to the general data, signs, symptoms, physical examination and laboratory values of each patient will be recorded daily in the data collection instrument. The record will be made on paper, which will be digitized and sent under encryption to the principal investigators every day.

As a quantitative method, the following laboratory findings will be considered to evaluate clinical progress, according to the requirement and availability of the hospital:

- Complete blood count
- C-reactive protein
- D-dimer
- Ferritin
- Procalcitonin
- Lactate
- AST

- ALT
- BUN
- Creatinine

Administration of thymic peptides (Unicahsina)

Thymic peptides (Unicahsina) will be administered in an oral dose of 250 mg per day. In the intubated patient, the administration will be done through a nasogastric tube. The presentation of thymic peptides (Unicahsina) will be in lyophilized form, which will be diluted in 50 ml of drinking water prior to administration. It should be administered on an empty stomach one hour before or two hours after a meal. If the patient is discharged, or if they need to be referred to an ICU, all the information will be gathered up to that moment and the administration of Unicahsina will be stopped.

Primary outcome measures

1) Time to participant recovery [Time Frame: During hospitalization for up to 20 days.]

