Measured in days to clinical recovery that will be defined as the first day, during the 20 days after enrollment, on which a patient met the criteria for category 1, 2, or 3 on the eight-category ordinal scale. The categories are as follows: 1, not hospitalized and no limitations of activities; 2, not hospitalized, with limitation of activities, home oxygen requirement, or both; 3, hospitalized, not requiring supplemental oxygen and no longer requiring ongoing medical care; 4, hospitalized, not requiring supplemental oxygen but requiring ongoing medical care (related to Covid-19 or to other medical conditions); 5, hospitalized, requiring any supplemental oxygen; 6, hospitalized, requiring noninvasive ventilation or use of high-flow oxygen devices; 7, hospitalized, receiving invasive mechanical ventilation or extracorporeal membrane oxygenation (ECMO); and 8, death.

2) Number of participants with treatment related adverse events as assessed by the Common Terminology Criteria for Adverse Events Version 5.0 (CTCAE v5.0) [Time Frame: Up to 20 days]

Number of participants who experience adverse events \geq Grade 3, as defined by the CTCAE v5.0.

3) Number of participants with treatment related side effects as assessed by the General Assessment of Side Effects (GASE) [Time Frame: Up to 20 days]

Number of participants who experience severe side effects as defined by the GASE.

Secondary Outcomes measures

1) Overall survival defined as the time from the start of treatment until death due to any reason [Time Frame: Up to 20 days]

Time for overall survival will be measured in days.

Other complementary analyzes

Computerized axial tomography and chest radiography

A Computerized tomography without contrast will be performed, with the patient in the supine position and the image acquisition will be carried out at the end of inspiration. The following parameters will be requested to obtain axial images: 1.25 mm thick, 1.25 mm interval, 120 kVp. If it is possible, chest radiographs will be requested in posteroanterior projection. However, in patients whose clinical condition warrants it, anteroposterior radiography will be considered. The images will be obtained at the moment of maximum inspiration, either with instruction to the patient or by controlling the ventilator console in the case of intubated patients.

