All quantitative data will be described using parameters such as the mean \pm standard deviation, or as the median (minimum and maximum). Qualitative data will be described by the number of cases (proportion%). Patient characteristics will be compared using the chi-square test or Fisher's exact test for categorical data. For continuous variable data, the Wilcoxon test or Student's t test will be employed. The analysis of time to a particular event will be carried out using the Kaplan-Meier method, and the analysis of differences between groups will be calculated with the log-rank test. The Cox proportional-hazard model will be used to estimate the hazard ratio and 95% confidence interval (CI). Propensity score matching methodology will be used to generate the comparison group from the clinical records. A p-value less than 0.05 will be required to establish significance. All analyses will be performed using SPSS and GraphPad Prism software.

SECTION 5 - ANONYMITY AND CONFIDENTIALITY OF DATA

The data will be obtained from the healthcare center assigned to treat positive cases of COVID-19, through the clinical record designed as an instrument for this study. The laboratory and imaging test reports, as well as the clinical records, will be digitized and sent to the principal investigators using the SOPHOS encryption software. This last part will ensure the confidentiality of each patient's data between devices while transferred. Access will be given to the Dirección General de Vigilancia del Marco Normativo de la Secretaría de Salud de Honduras (General Directorate for Regulatory Framework Surveillance of the Ministry of Health of Honduras) for the monitoring of the study. The hospital will have a password-protected electronic device. The access will be limited exclusively to medical doctors assigned for the study.

The physical documents will be attached to the patient clinical file at the end of the hospitalization.

For the data produced by CT or chest x-ray, the HOROS software will be used to visualize and anonymized DICOM files before sending them to radiologists. The confidentiality in transferring this information will be ensured by using the SOPHOS software.

SECTION 6 - POTENTIAL RISKS AND BENEFITS

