6.3 Describe the potential benefits

The administration of thymic peptides (Unicahsina) exerts an immunomodulatory effect, which will enhance the response of T, B and Natural Killer (NK) lymphocytes (51). This response is expected to help stop or mitigate the progression of alveolar destruction induced by the inflammatory reaction in the infection by Sars-Cov-2. The objective is to prevent progression to a more severe form of the disease, and consequently to reduce the mortality rate.

SECTION 7 - INCENTIVES AND INDUCEMENTS TO PARTICIPATE

7.1 Describe any incentive/inducement to participate that will be offered to the participants.

No incentives or inducements will be offered to participate in this study.

SECTION 8 - OTHER FINANCIAL CONSIDERATIONS

8.1 Describe the monetary expenses that the participants will incur.

The participants will not incur in any monetary expenses directly related with the study. The doses of the thymic peptides (Unicahsina), as well as the RT-qPCR tests, antigen or antibody test, CT scan and chest radiographs that are required as additional controls to those requested as a protocol by the Ministry of Health of Honduras will be financed by the State of Honduras, the Universidad Católica de Honduras and the Grupo de Investigacion Medica de la Universidad Católica de Honduras (GIMUNICAH).

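### The SAP does not say how deaths before recovery enter the time-to-recovery analysis; if patients are censored at the day of death, Kaplan-Meier overstates recovery by day 20 whenever a recovery falls on a later day than a death.

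*Combined protocol and SAP*

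**What the plan says.** All references are to Version B, the current text.

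- **Primary outcome measures.** Recovery is reached on the first day a patient is in one of the three best categories of an eight-category scale, within 20 days of enrolment. The scale ends with "hospitalized, receiving invasive mechanical ventilation or extracorporeal membrane oxygenation (ECMO); and 8, death".
- **Section 2.2.** Leavers are replaced "until 20 patients have reached conclusion either by medical discharge or death within a 20-day hospitalization follow-up". Death is therefore a foreseen way to complete follow-up. The same section plans to include elderly patients and those with comorbidities, and says of them: "The current COVID-19 pandemic has shown that this group of patients has the highest mortality rate".
- **Statistical Analysis Plan.** "The analysis of time to a particular event will be carried out using the Kaplan-Meier method". Group differences use the log-rank test, and a Cox model gives the hazard ratio with a 95% CI. The comparison group comes from hospital records by propensity score matching. The SAP has no censoring rule, names no competing-event method and does not mention death before recovery.
- **Secondary outcome.** Death is analysed only as the overall survival event.
- **Data cut-off.** Section 2.2 gives one for leavers: "Patient data will be used up to the date of voluntary withdrawal or self-discharge". It does not mention death.

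**The concern.** A patient who dies in hospital before recovery can never recover. Kaplan-Meier treats a censored patient as someone whose later course would resemble that of the patients still at risk. If follow-up for recovery ends at death, the curve gives patients who have died the recovery prospects of those still alive and unrecovered.

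Two analysts could follow the SAP to the letter and report different recovery curves for a primary outcome. One might end follow-up at death; the other might keep the patient as non-recovered to day 20.

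The choice also affects the comparison with the registry group. With deaths censored at death, the log-rank test and Cox model compare cause-specific recovery hazards. That is a legitimate quantity, but it does not describe the chance of recovering by day 20 when mortality differs between groups. Section 6.3 gives the aim of treatment as follows: "The objective is to prevent progression to a more severe form of the disease, and consequently to reduce the mortality rate". A difference in mortality is therefore what the plan hopes for.

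**Working it through.** The documents give no recovery rate, no in-hospital death rate and no derivation of the 20 participants, so there is no planned figure to reproduce. Every size below rests on assumptions.

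**1. Direction.** On a day with d recoveries among n patients at risk, the estimated recovery proportion rises by S(t−) × d/n. Aalen-Johansen takes S(t−) as the chance of being alive and unrecovered. Kaplan-Meier with deaths censored at death leaves the deaths out of S(t−), so its value is larger once a death has occurred. The two estimates therefore differ exactly when some recovery falls on a later day than some death. In 20,000 random data sets of 20 patients, Kaplan-Meier was higher in all 19,595 where this happened and equal in all 405 where it did not.

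**2. Size under constant hazards.** Let R be true 20-day recovery and D deaths before recovery by day 20.

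- Total hazard: H = −ln(1 − R − D)/20
- Recovery hazard: h = H × R/(R + D)
- Kaplan-Meier reading with deaths censored at death: 1 − exp(−20h)

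R = 70% is assumed. The first three values of D are borrowed from section 1.3 (all cases, over 70, over 80). They are general or age-group rates, not rates for this hospitalized population. The 20% is assumed outright.

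| D | H | h | Kaplan-Meier reading | Excess over 70% (points) |
|---|---|---|---|---|
| 2.3% | 0.06419 | 0.06214 | 71.1% | 1.1 |
| 8% | 0.07571 | 0.06794 | 74.3% | 4.3 |
| 14.8% | 0.09419 | 0.07775 | 78.9% | 8.9 |
| 20% | 0.11513 | 0.08954 | 83.3% | 13.3 |

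**3. Other time patterns.** True recovery is held at 70%. Recovery times among patients who do not die are exponential or lognormal (log-SD 0.5 or 0.8), and deaths are uniform over days 1–7, 1–20 or 11–20. Across the nine combinations the excess is 0.5–1.6, 1.9–6.0, 3.8–12.1 and 5.3–17.3 points at the four death rates. The median is too short by 0, 0–1, 0–2 and 0–2 days.

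**4. A data set of the planned size.** Assume 20 patients: 14 recover on days 4, 5, 6, 6, 7, 8, 8, 9, 10, 11, 12, 13, 15 and 17, three die, and three are alive and unrecovered at day 20. True recovery is 14/20 = 70.0% (exact 95% CI 45.7–88.1%), with median day 11.

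- Deaths on days 3, 5, 7: S(20) = (17/19) × (13/16) × (3/12) = 0.182, so the reading is 81.8%, median day 10.
- Deaths on days 12, 15, 18: S(20) = 0.45 × (7/8) × (6/7) × (4/5) = 0.270, so the reading is 73.0%, median day 11.
- Deaths on days 18, 19, 20, after the last recovery: 70.0%, median day 11, no excess.
- Deaths kept at risk and censored at day 20, whatever their dates: 70.0%, median day 11.

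**5. The contrast between groups.** Fix the recovery hazard at 0.07775 in every group, so the cause-specific hazard ratio is 1.0 and Kaplan-Meier reads 78.9% throughout. With assumed deaths of 8%, 14.8% and 22%, true 20-day recovery is 74.1%, 70.0% and 65.5%. A hazard ratio of 1.0 can therefore coexist with a real difference in recovery by day 20.

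**The case against.** **The text leans towards the harmless reading.** Section 2.2 lists death with medical discharge as a conclusion and attaches its data cut-off only to leavers. On the outcome scale, a patient who has died has plainly not reached a recovery category. This counts against inferring that the plan commits to censoring at death. But it is not a rule, and the SAP's bare reference to Kaplan-Meier leaves both codings open.

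**No 20-day recovery proportion is named as a result.** The outcome is measured in days and the planned effect measure is a hazard ratio. That stands: the point excesses concern the curve read at day 20, and the median moves by 0 to 2 days in the 70% recovery scenarios. But a Kaplan-Meier recovery curve over a 20-day window will be read at its end.

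**Random error is larger.** In the 20-patient example the excess of 0 to 11.8 points lies within the exact CI. At 2.3% mortality the chance of no death among 20 is 0.977^20 = 63%, and then there is no bias. This limits the weight of the point. The error is nonetheless systematic and avoidable.

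**Stronger readings the documents do not support.** A reader might infer that the log-rank test and Cox model are invalid; they remain valid for the cause-specific recovery hazard. A reader might infer that the comparison is tilted towards the treatment; that depends on the deaths in both groups, which the documents do not give. A reader might infer that any censoring of deaths is wrong; censoring at day 20 produces no excess when there is no other early censoring.

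**Conclusion.** The gap is real and worth closing, though it need not hold up the trial. The SAP gives no rule for deaths before recovery in a primary outcome. Under one natural coding, censoring at the day of death, recovery by day 20 is overstated whenever a recovery falls on a later day than a death. The direction of that excess is certain.

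Its size is not known. At 70% assumed recovery and constant hazards it runs from 1.1 to 13.3 points for assumed death rates of 2.3% to 20%. It depends on when deaths occur and is zero if none precedes a recovery. Nothing can be said about the direction of any between-group bias.

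Data that end for other reasons are outside this point. Section 2.2 already gives a cut-off for self-discharge. Whether outcome data stop at ICU referral is a separate matter: the section on administration says "if they need to be referred to an ICU, all the information will be gathered up to that moment", while the outcomes run to 20 days. Those passages must be reconciled on their own terms.

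**What to change.** State in the SAP that patients who die before recovery stay in the risk set as non-recovered and are censored at day 20, in both the treated and the matched registry group. This uses only the methods already named.

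The alternative is the Aalen-Johansen cumulative incidence of recovery, with death as a competing event and Gray's test. The two give the same recovery proportion when nobody else is censored early, but they can differ when there are withdrawals, so one should be chosen in advance.

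In either case, report the cause-specific Cox hazard ratio as a sensitivity analysis, and give the 20-day recovery and death proportions per group with exact 95% CIs. If the analysis has already been run, the rule used and these proportions can still be reported.

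The cost is SAP wording. The reported recovery rate may be somewhat lower than with censoring at death, a subdistribution measure is less familiar to clinicians, and Gray's test may need software beyond the two packages named.

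### Overall survival has no usable effect size if no treated patient dies, because an ordinary Cox hazard ratio is the only between-group measure planned with an interval

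*Combined protocol and SAP*

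**What the plan says.** Version B keeps one secondary outcome: "Overall survival defined as the time from the start of treatment until death due to any reason", with a time frame of up to 20 days. The treated group is small ("2.1 Number of participants: 20 participants"), and recruitment runs "until 20 patients have reached conclusion either by medical discharge or death within a 20-day hospitalization follow-up". The size of the comparison group and the matching ratio are not stated; the plan says only that "Propensity score matching methodology will be used to generate the comparison group from the clinical records".

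The Version B Statistical Analysis Plan names three tools for times to event. For description, "The analysis of time to a particular event will be carried out using the Kaplan-Meier method". For testing, "the analysis of differences between groups will be calculated with the log-rank test". For effect size, "The Cox proportional-hazard model will be used to estimate the hazard ratio and 95% confidence interval (CI".

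The first describes each group and the second gives a p-value. Only the third measures the difference between groups with an interval. Chi-square and Fisher tests are assigned to patient characteristics, not to death. The plan names no day-20 survival difference, no exact, penalised or profile-likelihood method, and no rule for a group without deaths.

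**The concern.** A Cox model needs deaths in both groups to give a finite hazard ratio. If every death is among the controls, the partial likelihood keeps rising as the hazard ratio falls towards 0, so there is no maximum and the Wald interval has no meaning. If every death is among the treated, the same happens in the other direction.

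No treated deaths is the best mortality result that this trial could show. It would leave the survival comparison with a p-value and two curves, but no effect size with limits. A rescue method would then be chosen after the deaths are known, which pre-specification is meant to prevent.

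**Working it through.** The plan gives no expected number of deaths, power or target hazard ratio, so it has no figure of its own to reproduce.

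**Inputs.** Treated group 20 (Version B, 2.1). Comparison group 20, an assumption. Follow-up 20 days. Control mortality p is not given for Stage IIb inpatients, so a range is used. One point in it comes from section 1.3, which gives 2.3% overall mortality and says "The disease is mild in 81% of cases, severe in 14% and critical in 5" per cent. If all deaths fall in severe or critical cases, p = 2.3 / (14 + 5) = 12.1%. The figure 14.8% is the background rate given there for cases over 80.

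**Does the estimate fail?** Take 0/20 v 4/20 deaths, with control deaths on days 4, 8, 11 and 15 (illustrative) and everyone else followed to day 20. The risk sets hold 20 treated patients and 20, 19, 18 and 17 controls. With b the log hazard ratio, the log partial likelihood is −Σ log(20·e^b + n), n = 20, 19, 18, 17.

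- b = −1: −13.007
- b = −5: −11.693
- b = −10: −11.66395
- b = −20: −11.66376, which is the limit −log(20 × 19 × 18 × 17)

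It never turns down. A standard fit did not converge: b was about −48, the standard error about 10^10, and the Wald 95% CI for the hazard ratio 0 to infinity. With 1/20 v 4/20 the fit is finite: 0.23 (0.03 to 2.10).

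**How often?** With hazard ratio HR, treated mortality is 1 − (1 − p)^HR. So P(no treated deaths) = (1 − p)^(20·HR), P(no control deaths) = (1 − p)^20, and P(at least one group has none) = 1 − (1 − first)(1 − second). At 12.1% and HR 0.5: 0.879^10 = 0.275, 0.879^20 = 0.076, and 1 − 0.725 × 0.924 = 0.33.

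| Control mortality | No treated deaths, HR 0.5 | At least one group with none, HR 0.5 | At least one group with none, HR 1 |
|---|---|---|---|
| 12.1% | 28% | 33% | 15% |
| 14.8% | 20% | 23% | 8% |
| 20% | 11% | 12% | 2% |
| 30% | 3% | 3% | 0.2% |

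Simulation at 12.1% and HR 0.5 agrees (32%). In it, about 84% of the trials with a significant log-rank test had a group without deaths; that share falls steeply as mortality rises. A larger comparison group helps little: at 14.8% and HR 0.5 the chance is still about 20% with 40 or 60 controls, because the treated group drives it.

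**What stays estimable at 0/20 v 4/20?**

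- Ordinary profile likelihood: upper limit for the hazard ratio about 0.57, no lower limit above 0.
- Firth: add ½·log Σ q(1 − q) to the likelihood above, with q = 20·e^b / (20·e^b + n). The maximum is at a hazard ratio of about 0.10, and the profile drops by 3.84/2 at about 0.0008 and 0.96.
- Log-rank: p = 0.037. The permutation version gives 0.106, equal to Fisher's exact test: 2 × C(20,4)/C(40,4) = 2 × 4,845/91,390.
- Newcombe interval for the risk difference of −20 points: −41.6 to +0.1, valid only if day-20 vital status is known for all.
- For 0/20 alone, the exact 95% upper limit for the risk of death is 1 − 0.025^(1/20) = 16.8%.

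**The case against.** The strongest reply is that this touches one effect measure for one secondary outcome and may seldom arise. Much of that stands.

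- **Mortality would still be reported.** A reader might infer that the trial could end without a mortality result. The plan also provides counts and proportions, Kaplan-Meier curves and a log-rank test, and all of these work with no deaths in one group. Time to recovery does not depend on the survival model.
- **The frequency is not known.** A reader might take 12.1% as the documents' inpatient mortality. It is not: it assumes that all deaths fall in severe or critical cases and that this mix resembles the trial's patients, whereas enrolment uses the Ministry of Health's Stage IIb definition. At 30% mortality the problem is uncommon unless the effect is large.
- **No control deaths is the opposite case.** The chances for at least one group include it; the column for no treated deaths is the one that matters when the drug looks good.
- **Width is not the Cox model's fault.** With four or five deaths any method gives wide limits, as the Newcombe interval shows.
- **The log-rank test is not generally unreliable.** Its simulated false-positive rate was 4.7% to 5.1% at 12% to 30% mortality. The gap between 0.037 and 0.106 shows only that single results with very few deaths can depend on the large-sample approximation.
- **Simple day-20 proportions are not a free replacement.** Version B section 2.2 uses data only to withdrawal or self-discharge, and the section on administration of thymic peptides gathers information only up to discharge or ICU referral. Proportions would need vital status beyond those points.

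None of this supplies an effect size when no treated patient dies.

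**Conclusion.** The point holds as a cheap improvement, not as an error that invalidates the analysis. For overall survival, the only planned effect measure with an interval has no usable value when one group has no deaths. Assuming 20 v 20 and a true hazard ratio of 0.5, the chance is about a third at 12% control mortality, 12% at 20% and 3% at 30%, and nearly all of it comes from no treated deaths. These figures rest on an assumed comparison-group size, an assumed mortality range and complete follow-up to day 20. Stopping information at ICU referral could lower the observed deaths and raise the chance.

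**What to change.** Keep the time-to-event analysis and change how the effect is estimated. For overall survival, the SAP should state:

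1. The hazard ratio is estimated by Firth-penalised Cox regression with a profile-likelihood 95% CI. This stays usable with no deaths in one group.
2. Deaths per group are reported, with Kaplan-Meier survival at day 20 per group and a small-sample interval that allows for censoring.
3. When deaths are very few, an exact or permutation log-rank p-value is given as a sensitivity check. It is needed beside item 1: in the 0/20 v 4/20 example the Firth interval just excludes 1 while the exact p-value is 0.106.
4. A plain 20-day risk difference with a Newcombe interval is used only if day-20 vital status is known for everyone. Otherwise it is labelled as observed in-hospital deaths. If matching is 1:1, the paired form is used.

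The cost is a few sentences, probably one free package beyond SPSS and GraphPad Prism, and slight shrinkage of the hazard ratio. No new data are needed for items 1 to 3. The change does not reduce the imprecision that comes from few deaths, and it does not remove any bias from cutting information at discharge or ICU referral.
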